2.1 Primary endpoint

- Early patient reported gastro-oesophageal toxicity measured as peak score within the first 5 weeks after treatment start measured by PRO-CTCAE, see Appendix A.

2.2 Co-primary endpoint

- Ambulatory function: Preserved ability to walk measured by EQ-5D-5L, see Appendix B.

2.3 Secondary endpoints

- Duration of gastro-oesophageal toxicity
- Reirradiation rate
- Preserved physical function measured by EORTC QLQ C30, see Appendix C.
- Changes in Quality of life (QoL) measured with EQ-5D-5L and EORTC QTQ C30
- Change in weight
- Pain reduction (MTS site) from baseline evaluated by “Numeric Pain Rating Scale (NPRS)”, see Appendix D.
- Change in analgesic consumption
- Overall survival (OS)
- Incidence of glucocorticoid induces diabetes
- Incidence of glucocorticoid induced diabetes treated with insulin
- Number of patients with normalized blood-glucose values on day 28 after start of treatment
- Incidence of hospital contacts requiring regulation of hyperglycemia
- Incidence of hospital admissions due to new-onset diabetes
- Time in range
- Time above range
- Time below range
- Mean glucose
- Standard deviation
- Coefficient of variation

2.4 Definition of endpoint related concepts

- The duration of patient reported gastric-oesophageal toxicity is measured as the time from an increase in gastro-oesophageal symptom score to a return to baseline
- Reirradiation rate is defined as fraction of patients getting reirradiation, where the same spine levels are included in the irradiated volume
- OS is defined as time from inclusion until death from any cause
- diabetes developed during glucocorticoid treatment will be defined as two random plasma glucose measurements $\geq 11,1$ mmol/L.
- Time-in-range is defined as the percent of time glucose value is in normal range (3,9-10 mmol/L)
- Time above range is defined as the percent of time the glucose value is above normal range
- Time below range is defined as the percent of time the glucose value is below normal range
- Coefficient of variation for glucose is calculated as **(Standard Deviation / Mean) * 100**

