1.3 Glucocorticoid-induced diabetes

High dose glucocorticoid is used in MSCC to decrease inflammation and edema in the affected vertebra and neural tissue. In our clinic, patients are started on high-dose glucocorticoids (150 mg Prednisolone daily) when MCSS is suspected. During radiotherapy the dose is reduced to 75 mg daily. A minimum 5 days of treatment are mandatory, even for patients treated with single fraction. High-dose glucocorticoid treatment may be discontinued after 5 days or after end of radiotherapy treatment, whichever comes first. Depending on symptoms and duration of prior glucocorticoid treatment some patients may benefit from a gradual decrease. ^{12,13}

It is well established that glucocorticoid treatment can induce new-onset hyperglycemia and even glucocorticoid-induced diabetes mellitus (GIDM) in patients without a history of diabetes mellitus (DM) ¹⁴. Hyperglycemia has been associated with complications such as longer hospital stays, delayed wound healing, increased infections and higher mortality rates. ¹⁴

As of now there are only two studies describing glucocorticoid-induced diabetes in patients receiving treatment for MSCC. ^{15,16} Schultz et al performed a prospective study including 131 patients receiving high-dose glucocorticoids for MSCC. The patients were monitored with 1-3 finger prick glucose measurements for 12 days after treatment start. 43% of the patients presented plasma glucose values diagnostic of diabetes and 12% were treated with insulin¹⁵. A HbA_{1c}-value <39 mmol/mol was associated with a negative predictive value of 96% for not developing diabetes needing treatment with insulin.¹⁵

While insulin-treated diabetes was mainly diagnosed in the first week after treatment start, the incidence of non-insulin treated diabetes was rising through-out the study period¹⁵. There are no data describing glucose levels beyond the study period of 12 days.

[figure not shown]

Figure 3 Time course of development of diabetes¹⁵

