2.6 HbA_{1c} validation

Baseline HbA_{1c} is measured for all patients starting high glucocorticoid treatment for MSCC. Baseline values above 48 mol/mol are considered diagnostic for DM. For all other patients, diabetes developed during glucocorticoid treatment will be defined as two random plasma glucose measurements ≥ 11 mmol/L. Based on baseline HbA_{1c} results and subsequent glucose measurements from the patients included in ESO-SPARE we will validate if the current HbA_{1c} cut off value (39 mmol/mol) can identify patients in low risk of developing glucocorticoid-induced insulin-dependent DM.

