6.4 Esophagus sparing radiotherapy vs. standard treatment

For the patients in the standard arm, a standard radiotherapy plan computed using VMAT technique aiming at covering the PTV with at least 90 % of the prescribed dose and not taking the dose to the esophagus and/or stomach into account.

For the patients in the interventional arm, a plan using VMAT technique is computed aiming at keeping the maximum dose to the esophagus and/or stomach as described in Table 4. Even if it means compromising the dose to the PTV and CTV.

Patients randomized to esophagus sparing radiotherapy needing reirradiation (**other target that primarily prescribed**) during the 9 weeks of FU, will receive esophagus sparing radiotherapy for the second target.

	Maximum Physical Esophageal Dose ($D_{0,027\text{cm}^3}$) (Gy)		Max. Esophageal Dose in EQD2 ($D_{0,027\text{cm}^3}$) (Gy), $\alpha/\beta = 3$ Gy	
Fractionation (Dosis (Gy) x Fraction)	Standard arm	Esophagus sparing arm	Standard arm	Esophagus sparing arm
5 Gy x 5	25	8,5	40	8
3 Gy x 10	30	10	36	8
10 Gy x 1	10	5	26	8
8 Gy x 1	8	5	17,6	8

Table 4. Maximum esophageal dose. Standard arm vs. esophagus sparing arm.

7 HbA_{1c} and Flash glucose monitoring

HbA_{1c} will be measured at baseline, which is standard procedure in one of the participating centers.

²³ In order to obtain ambulatory glucose profiles for retrospective glucose data analysis we will use a blinded professional sensor-based Flash glucose monitoring system (FreeStyle Libre Pro™; Abbott Diabetes Care, Witney, UK).^{19,20} The sensor is worn on the upper arm for 14 days. The sensor is factory calibrated which means that, after activating the sensor at baseline, no further intervention during the 14-day wear is required. As the sensor is blinded, data are not visible to participants or investigators during sensor wear. The sensor automatically captures and stores glucose data every 15 min (96 glucose readings/day). After 14 days the sensor is dismantled, and glucose data are wirelessly transferred to the pro-reader. Summary glucose reports are generated using the system software. Patients in our study will be followed for 28 days after start of radiotherapy treatment requiring one sensor change. This will include time without glucocorticoid treatment.

The patients participating in this part of the study will not be subject to standard glucose measurements; instead they will be thoroughly instructed to contact the PI if symptoms of hyperglycaemia should occur.

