9.1 Ethical considerations

The focus of this study is palliation with reduction of side effects from necessary radiation therapy for MSCC. The study participants are fragile with low life expectancy.^{2,5} In order to minimize the time, spend in hospital, we designed the study with electronical/telephone follow-up only.

All toxicology data will be collected as patient reported outcomes (PRO). All though we will not act directly the collected PRO, the patients will be encouraged to contact the department with any problems there might occur.

In order to compute a radiation plan with sparing of the esophagus for patients in the experimental arm, it might be necessary to compromise the dose delivered to the anterior part of the vertebra close to the esophagus. While we do not expect the treatment in the experimental arm to be less effective, it is one of the objectives of this study to examine this. Reirradiation rates in the two arms will be assessed continuously. The TMC can recommend cessation of the study or dose adjustments if the reirradiation rate in the experimental arm is to excessive.

There will be no extra radiation from extra scans in this study.

In order to determine the natural course of plasma-glucose during and after high-dose glucocorticoid treatment, we wish to perform a real-life study with as little intervention as possible. Therefore, we intend to use blinded glucose measurements only. For study participants 1-2 fewer glucose measurements pr. week compared to current standard is expected. Patients participating in

the study by Schultz et al received 300 mg Prednisolone daily for 10 days, which was local standard at the time.¹⁵ The guidelines have since been modified and currently recommended Prednisolone doses as well as duration of treatment is significantly lower.¹³ Because of this, we expect the incidence of glucocorticoid induced hyperglycemia and diabetes to be lower in our study population.

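### Glucocorticoid-induced diabetes is defined by two random plasma glucose values, which sensor participants are not scheduled to give, and no rule is set for the sensor readings that replace them

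*Protocol*

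**What the plan says.** Protocol section 2.3 lists "Incidence of glucocorticoid induces diabetes" as a secondary endpoint. Section 2.4 gives the definition: "diabetes developed during glucocorticoid treatment will be defined as two random plasma glucose measurements", with a threshold of 11.1 mmol/L. Section 2.6 repeats it as "two random plasma glucose measurements ≥ 11 mmol/L", so the threshold differs slightly between the two sections. Section 2 also asks how many patients who develop this diabetes have normal values by day 28, so that question takes its denominator from the same definition.

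Section 7 describes how glucose is observed. "The patients participating in this part of the study will not be subject to standard glucose measurements"; they contact the investigator if symptoms appear. Section 9.1 gives the intent: "Therefore, we intend to use blinded glucose measurements only". Under sections 4.1 and 4.2, other glucose measurements depend on symptoms or admission and on the judgement of the clinicians involved. Section 7 also says: "The sensor automatically captures and stores glucose data every 15 min (96 glucose readings/day". Wear lasts 28 days over two sensors and includes time off glucocorticoid.

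The SAP contains no glucose endpoint.

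**The concern.** The definition and the data source do not meet. The definition needs plasma values, and the design removes their routine collection from the patients in whom the glucose course is to be described. An analyst could follow either of two readings.

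- **Plasma only.** A patient can qualify only if someone had a reason to sample. A patient with raised glucose and no symptoms, not admitted, cannot be counted.
- **Sensor values in place of plasma.** The rule was written for sparse samples. On a trace stored every 15 minutes, two neighbouring readings from one post-meal rise satisfy it.

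Under both, the reported incidence depends heavily on how often glucose was read, and the day-28 denominator inherits the problem. Section 9.1 expects a lower incidence than the earlier finger-prick study, which found 43% (section 1.3). The first reading could confirm that expectation because few samples were taken. The second could contradict it because many were.

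**Working it through.** **Reading counts.** Section 7 gives 96 readings a day: 24 × 60 / 15 = 96, which reproduces. Complete 28-day wear gives 28 × 96 = 2,688. The definition is limited to glucocorticoid treatment, and section 1.3 sets a 5-day minimum, so the on-treatment count can be as low as 5 × 96 = 480.

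**Earlier study.** Section 1.3 reports: "The patients were monitored with 1-3 finger prick glucose measurements for 12 days after treatment start". Reading 1-3 as a daily number is an assumption; it gives 12 to 36 values per patient.

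**Plasma-only reading.** The number of scheduled plasma values in a sensor participant is zero. No arithmetic is needed to see that ascertainment depends on symptoms and admission.

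**Sensor reading.** The documents give no distribution of sensor glucose, so everything below is illustration. Assume log-normal glucose with mean 7.0 mmol/L, CV 25% and correlation decaying over about 2 hours.

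- Log-variance = ln(1 + 0.25²) = 0.0606, SD 0.246; log-mean = ln 7.0 − 0.0303 = 1.916.
- Share of readings at or above 11.1: z = (2.407 − 1.916) / 0.246 = 2.00, so p = 2.3%.
- For n well-separated values, P(at least 2) = 1 − (1 − p)^n − n·p·(1 − p)^(n−1). With p = 0.023 and n = 12, this is 1 − 0.756 − 0.214 = 3%. With n = 24 it is 10%. With n = 36 it is about 20% (21% by simulation).
- Sensor readings are correlated, so that formula does not apply to them and the traces were simulated.

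Probability of at least two values at or above 11.1 mmol/L:

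| Assumption | Finger prick, 12 days | Sensor, 5 days | Sensor, 28 days |
|---|---|---|---|
| Mean 7.0, CV 25%, all patients alike | 3%, 10%, 21% (1, 2, 3 a day) | 93% | 100% |
| Same, half the log-variance between patients | 5-15% | 39% | 61% |
| Mean 6.5, CV 20%, all patients alike | 0.1-0.6% | 27% | 89% |

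The sensor figures carry simulation error of a few percentage points.

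**Calibrated check.** A second set of autocorrelated traces, with a daily swing and three levels of between-patient spread, was tuned to a chosen incidence on two finger pricks a day for 12 days:

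| Tuned finger-prick incidence | Sensor, 5 days | Sensor, 28 days |
|---|---|---|
| 43% | 47-66% | 57-93% |
| 20% | 25-45% | 34-80% |
| 10% | 13-26% | 19-61% |

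The sensor figure exceeds the finger-prick figure in every row of both tables, even with 5 sensor days against 12 finger-prick days. The 28-day columns hold glucose at its on-treatment level throughout, so they are upper illustrations.

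**The case against.** A reader might infer that the sensor would label almost every participant diabetic. The documents do not support that. Section 1.3 says the glucose course in these patients has not been described. The 100% figure needs identical glucose distributions in all patients and all 28 days counted, although part of that time is off treatment. Patients clearly differ: section 1.3 reports that 12% in the earlier study received insulin and that HbA1c was informative about who would. Allowing for that spread brings the same setting down to 61% over 28 days and 39% over 5. The uncalibrated illustration also gives only 3-21% by finger prick, well short of the observed 43%.

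A reader might also infer that the study would miss silent hyperglycaemia altogether. It would not. Time above range, mean glucose, standard deviation and coefficient of variation are separate sensor endpoints. They do not use the two-value rule, and neither does the insulin-treated outcome. No formal comparison with 43% is planned either; section 9.1 states an expectation in an ethics discussion.

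Section 9.1 also expects only 1-2 fewer measurements a week than standard, which might suggest that some routine sampling remains. But Tables 5 and 6 give a standard of none to twice weekly for patients with HbA1c below 48 mmol/mol and no raised values. The phrase is therefore compatible with removing routine sampling entirely, as section 7 says.

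These points limit the size and reach of the problem. They do not supply the missing rule.

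**Conclusion.** The gap stands on the text alone: the endpoint is defined on values that sensor participants are not scheduled to provide, and nothing adapts the definition to the data they do provide. The direction is low under the plasma-only reading and, relative to finger-prick sampling, high under the sensor reading. The size is not known. The illustrated sensor incidence runs from 13% to 100% across the settings shown, and it rests on an assumed mean, spread, autocorrelation and on-treatment window.

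What is affected is the incidence of glucocorticoid-induced diabetes and the day-28 normalization denominator. Both are secondary, but incidence is one of GLUC-DIAB's stated research questions. Under either reading, a difference from 43% could not be attributed to the change in glucocorticoid regimen. The 11.1 and 11 mmol/L thresholds are a plain inconsistency between sections 2.4 and 2.6.

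**What to change.** In sections 2.4 and 2.6:

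- State that incidence in sensor participants is computed from sensor data within a stated on-glucocorticoid window. Define that window from each patient's own treatment dates, since a fixed number of days can run past the end of a short course. Say how steroid days before sensor placement are handled, because steroids start when compression is suspected (section 1.3) and the sensor goes on after the planning CT (section 6.1).
- Prespecify a rule that one excursion cannot meet: for example, sensor values at or above the threshold at fixed clock times on two different days. Fix the number of draws per day in advance, because the result still depends on it (3% with one and 21% with three in the illustration).
- Report diabetes detected from routine-care plasma values as a separate endpoint and do not pool the two. Outside the sensor group, Table 5 schedules no measurements at one centre when HbA1c is 39 mmol/mol or lower, while Table 6 has twice-weekly measurement for all at the other. Pooling would tie detection to centre and to HbA1c, the predictor under validation.
- Make no direct comparison with 43% unless the sampling is matched.
- Reconcile the threshold between the two sections.

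The cost is a few sentences and a short analysis script, with no new samples. The downside is that interstitial readings stand in for plasma values, and the report must say so.

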2.5 Pain assessment and the numeric pain rating scale (NPRS)

In the conventional radiation setting, the International Consensus Pain Response Endpoints (ICPRE) has been developed for clinical endpoints as pain for bone metastases²¹. In this protocol, we will use the ICPRE to evaluate pain response. Response categories are based on patient reported pain scores (NPRS) and analgesic consumption (convert to oral morphine-equivalent dose).

NPRS ranges from '0' representing one pain extreme (e.g. "no pain") to '10' representing the other pain extreme (e.g. "pain as bad as you can imagine" or "worst pain imaginable"). See Appendix C.

Registration of NPRS will be registered at baseline and subsequently according to Table 2. Analysis of pain reduction will only include patients with $\text{NPRS} \geq 1$ registered at baseline. We intend to report the best response during follow-up. If more than one lesion is treated, the index lesion will be used to assess the pain response. The index lesion is defined as the lesion with the highest pretreatment pain score. If a patient has two or more lesions with the same maximum pain score, the index lesion is defined as the most cranial located lesion.

- A complete pain response is defined as a pain score of 0 out of 10 at the treated site with no concomitant increase in analgesic intake
- A partial pain response is defined as a pain reduction of 2 or more at the treated site without analgesic increase, or an analgesic reduction of 25% with no increase in pain score or 1 point above baseline.
- Pain progression is defined as an increase in pain score of 2 or more above baseline with stable analgesic intake or an analgesic increase of 25% with stable pain score.
- An indeterminate response is any response not captured in the above definitions.

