For each of the first five weeks, where daily measurements are recorded, the peak value will be used for analysis. Changes in severity score over time (repeated measurement) will be analyzed using Generalized Linear Mixed Models.

C. Duration of dysphagia, nausea and dyspepsia measured by NCI-PRO-CTC-AE [Time Frame: within five weeks after start of RT (daily measurements) and at 6, 7, 8, and 9 weeks].

Duration of toxicity will be presented graphically in separate figures.

For the first five weeks mean duration (days) in each group will be compared using Wilcoxon rank-sum test.

D. Severity of cough, oropharyngeal pain, dyspnea, dysphagia, hoarseness, and dyspepsia measured by CTC-AE (weekly measurements) [Time Frame: Week 1-5 after start of radiotherapy (repeated measurement)].

CTC-AE responses are scored from 0 to 4, with 0 representing “None” and 4 representing “Very severe”.

Changes in severity score over time (repeated measurement) will be analyzed using Generalized Linear Mixed Models.

E. Duration of cough, oropharyngeal pain, dyspnea, dysphagia, hoarseness, and dyspepsia measured by CTC-AE (weekly measurements) [Time Frame: Week 1-5 after start of radiotherapy (repeated measurement)].

Duration of toxicity will be presented graphically in separate figures. Mean duration (weeks) in each group will be compared using Wilcoxon rank-sum test.

F. Demographics: Subject demographics, baseline characteristics and medical history will be summarized descriptively. Generally, range, mean and standard deviation, or median and inter quartile range, will be reported for continuous variables. Frequencies and proportions will be reported for categorical variables.

G. Treatment site pain response [Time frame: weekly, 1-9 weeks after start of RT]:

Only patients with baseline pain will be included in the analysis.

Pain response will be measured by the ICPRE score (6). Possible responses are “Complete response”, “Partial response”, “Pain Progression” and “Intermediate response”.

For each of the first five weeks, where daily measurements are recorded, the worst response will be used for analysis. Changes in ICPRE score over time (repeated measurement) will be analyzed using Generalized Linear Mixed Models.

H. Duration of treatment site pain response [Time Frame: Weekly week 1-9 after start of radiotherapy].

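### The partial pain response definition in protocol 2.5 counts a patient one point worse on 25% less analgesic as a responder, the progression rule has no matching allowance, and the SAP does not write out the categories

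*Protocol*

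**What the plan says.** Protocol 2.5 adopts the International Consensus Pain Response Endpoints (ICPRE) and then writes out four categories.

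- Partial response, pain route: "A partial pain response is defined as a pain reduction of 2 or more at the treated site without analgesic increase".
- Partial response, analgesic route: "an analgesic reduction of 25% with no increase in pain score or 1 point above baseline".
- Progression: "an increase in pain score of 2 or more above baseline with stable analgesic intake or an analgesic increase of 25% with stable pain score".
- Everything else: "An indeterminate response is any response not captured in the above definitions".

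For the summary over time, protocol 2.5 says "We intend to report the best response during follow-up".

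SAP analysis G states "Pain response will be measured by the ICPRE score (6", the 6 being the reference number of the consensus paper. It lists four category names without defining them, and calls the fourth one intermediate where the protocol says indeterminate. For the summary over time, analyses G and H say "For each of the first five weeks, where daily measurements are recorded, the worst response will be used for analysis".

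Pain response is a secondary endpoint. SAP purpose 2 compares it between arms, and SAP analysis O correlates it with target coverage.

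**The concern.** A response category should not admit a score above baseline in the same clause that rules out an increase. A programmer has to choose which half governs, and the SAP gives no definition to choose by, so the choice could be made after data are in.

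The one-point allowance is also written on one side only. It creates responders, while the progression rule has no counterpart for a patient who is one point worse and needs more analgesic.

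This matters because the sparing plan may give up dose to the PTV and CTV (protocol 6.4). Pain response is one of several outcomes on which a resulting loss of effect might show. Analgesics are prescribed at the referring physician's discretion (protocol 4.4) and only patients are blinded, so the analgesic route needs a clear pain condition.

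**Working it through.** **The plan's own figures.** No sample size or power figure uses the pain definition. The stated power for ambulatory function (84%, 66 evaluable per arm, Wilcoxon rank-sum) reproduces at 83.1% in 4,000 simulated trials from the tabulated distributions (22/44/26/8 against 11/32/37/20, two-sided 0.05). Exact Fisher power for 0.6 against 0.3 with 62 per arm is 0.91, against the stated 0.9. Neither depends on the wording at issue.

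**The rule applied literally.** Stable is read as unchanged, and the follow-up score is above 0.

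| Change in NPRS | Analgesic −25% | Analgesic unchanged | Analgesic +25% |
|---|---|---|---|
| 0 | partial | indeterminate | progression |
| +1 | **partial** | indeterminate | **indeterminate** |
| +2 | indeterminate | progression | indeterminate |

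The +1 row shows the asymmetry: one point worse is a response when analgesic falls by 25%, but is not progression when analgesic rises by 25%.

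**How much of the rule the clause touches.** Baseline 1–10, follow-up 0–10 and three analgesic changes give 10 × 11 × 3 = 330 combinations. Removing the one-point alternative changes 9 of them (baselines 1 to 9, score up by exactly 1, analgesic down 25%), all from partial to indeterminate. Nothing changes with stable or increased analgesic, or with a rise of 2 or more.

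**Effect on a response rate.** At any one assessment the rate rises by the share f of analysed patients in that cell. The documents do not give f. If f is assumed to be 0–10%, the inflation is 0–10 percentage points.

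**Effect on a difference between arms (illustration; every input is assumed).** True pain is uniform on 2–8, and reported NPRS is rounded and limited to 0–10 with error SD 0.7, 1.0 or 1.5. One arm is unchanged, the other truly 1 point worse, and both are scored by the same rule. Among patients who cut analgesic by 25%:

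| Error SD | Gap without the clause | Gap with the clause | Loss |
|---|---|---|---|
| 0.7 | 37 points | 24 points | 13 |
| 1.0 | 64 − 37 = 27 points | 85 − 64 = 21 points | 6 |
| 1.5 | 18 points | 16 points | 2 |

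If 20–30% of patients cut analgesic, the loss across all patients is between 0.20 × 2 = 0.4 and 0.30 × 13 = 3.9 percentage points. The model takes cutting analgesic to be unrelated to worsening pain.

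**Summary over time.** Under the protocol's best-response rule one qualifying reading is enough, which enlarges the effect of the clause. Under the SAP's weekly worst-response rule every reading in the week must qualify, which shrinks it. The two rules therefore give different answers from the same diary.

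**The case against.** The strongest defence is that the clause is a measurement tolerance. Protocol 2.5 already treats one point as too small to count: the pain route needs a fall of 2 and progression a rise of 2. Stable pain score is undefined in the progression rule, and if it includes a one-point rise the asymmetry disappears. This is a possible intention, but it is not written. As a tolerance the clause still makes its own first condition redundant, and the plan nowhere says what stable means.

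The objection stands against several stronger readings that a reader might infer:

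- *Any patient with worse pain can be a responder.* No. The 25% analgesic reduction is also required, and a rise of 2 or more never qualifies.
- *The trial's safeguard against under-dosing is compromised.* No. The declared check is ambulatory function (protocol 3.4), and the trial management committee watches reirradiation (protocol 8.3 and 9.1). Worsening could also show in the protocol's separate endpoints for pain reduction and analgesic consumption, and in the pain items of EQ-5D-5L and QLQ-C30.
- *The clause favours the sparing arm or conceals its loss.* Not shown. It applies to both arms. Setting a worse arm scored with the clause (64%) beside a stable arm scored without it (64%) compares two different rules; under one rule the gap shrinks but remains.
- *Patients with baseline NPRS 1 should be excluded.* The protocol says "Analysis of pain reduction will only include patients with" a baseline NPRS of at least 1, and raising this to 2 has no basis in the categories. A patient at 1 can be a partial responder by the analgesic route, and a fall from 2 to 0 is already complete, so a partial response by pain reduction alone needs a baseline of 3 or more. For a stable true score of 1 (assumed error SD 0.5–1), one reading of 0 has probability p = Φ(−0.5/SD) = 0.159–0.309. A false complete response at some point in nine independent readings then has probability 1 − (1 − p)^9 = 79–96%, but only under best response. Under the SAP's worst-response rule with three readings in a week it is p³ = 0.4–3%.
- *The wording departs from the cited consensus.* This cannot be judged from the documents.

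**Conclusion.** The concern holds as a defect of definition in a secondary endpoint. The analgesic route contradicts itself and, as written, counts a patient one point worse on 25% less analgesic as a responder. The absence of a matching allowance for progression depends on reading stable as unchanged. The SAP corrects neither point.

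The consequence is a looser endpoint in both arms, with some dilution of the between-arm pain comparison and of the target-coverage correlation. On the assumed inputs the dilution is about 0.4 to 4 percentage points across all patients. The documents contain no figure from which the true size could be derived. The co-primary endpoints and their power are unaffected. It should be corrected because correction is easy and leaving it open invites a choice made after the data are seen.

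**What to change.** 1. In protocol 2.5, delete the closing alternative in the analgesic route, so that a score above baseline is never a response.
2. In the progression rule, define stable and state how a one-point rise is treated, including when analgesic use has increased.
3. Check the four categories against the cited consensus, then write them out in SAP analyses G and H in the same words and with the same names as the protocol.
4. Reconcile the protocol's best-response summary with the SAP's weekly worst-response summary: state which one is the reported endpoint and, if both are kept, what each is for.

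The baseline NPRS requirement can stay as it is. The cost is a few lines of text and a change to the derivation, with no new data or patients. Response rates will be slightly less favourable in both arms.
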